**10.3.3.2. Effectiveness (Responder-based): rMenB+OMV NZ - 3 doses (0,2,6-months schedule)**

Analysis set: FAS will be the primary analysis population.

Statistical method: The percentage of responders (see definition in Section 10.1.1.2) and the corresponding exact two-sided 97.5% CI based on Clopper-Pearson method will be calculated [Clopper, 1934].

The objective is to demonstrate that the lower limit of the 97.5% CI for the percentage of responders is higher than 65%.

**10.3.3.3. Vaccine effectiveness (Test-based): rMenB+OMV NZ - 2 doses (0,6-months schedule)**

See Section 10.3.3.1

**10.3.3.4. Effectiveness (Responder-based): rMenB+OMV NZ - 2 doses (0,6-months schedule)**

See Section 10.3.3.2

**10.3.3.5. Vaccine effectiveness (Test-based): rMenB+OMV NZ - 2 doses (0,2-months schedule)**

See Section 10.3.3.1

**10.3.3.6. Effectiveness (Responder-based): rMenB+OMV NZ - 2 doses (0,2-months schedule)**

See Section 10.3.3.2

**CONFIDENTIAL**205416 [MENB REC 2ND GEN-038 (V72\_72)]  
Protocol Amendment 4 Final**10.3.3.7. Lot-to-lot consistency: MenABCWY - ACWY component**

Analysis set: The analysis of lot-to-lot consistency will be based on the PPS.

Statistical method: For each of the three ABCWY lots (Lots 1, 2 and 3 of the MenACWY component of the ABCWY vaccine), GMTs and 97.5% CIs will be calculated by exponentiating (base 10) the least squares means and the lower and upper limits of the 97.5% CIs of the log transformed titres (base10) obtained from a two-way Analysis of Variance (ANOVA) with factors for vaccine lot and study centre. Additionally, lot-to-lot GMT ratios will be computed for each pair of ABCWY lots. Ninety-seven point five percent (97.5%) CIs for the ratios of GMTs will be constructed by exponentiating the difference of the least square means of the log transformed titres and the lower and upper limits of the 97.5% CIs on the difference obtained from the ANOVA model above.

Lot-to-lot consistency criterion: The three ABCWY lots will be considered equivalent if for each of the 4 serogroups A, C, W and Y and each pair of vaccine lots, the two-sided 97.5% CI on the ratio of GMTs at 1 month after the last vaccination will be contained within the interval [0.5, 2.0]

**10.3.3.8. Immunological non-inferiority: MenABCWY vs. MenACWY in subjects without a previous MenACWY vaccination (unprimed)**

Analysis set: PPS will be the primary analysis population.

Statistical method: The percentage of subjects with 4-fold rise in hSBA titres against MenACWY indicator strains A, C, W and Y and the corresponding exact two-sided 97.5% CIs based on Clopper-Pearson method will be calculated for the ABCWY (pooled lots) group and the ACWY group [Clopper, 1934]. The 97.5% CIs for the difference in percentages between ABCWY (pooled lots) and ACWY group will be constructed using the method of Miettinen and Nurminen [Miettinen, 1985].

Non-Inferiority criterion: Non-inferiority of MenABCWY vaccine for the proportion of subjects with 4-fold rise will be demonstrated if the lower limit of the two-sided 97.5% CI for the difference in percentage of subjects with 4-fold rise between the 2 groups (ABCWY (pooled) lots –ACWY) is above -10%.

**10.3.3.9. Vaccine effectiveness (Test-based): MenABCWY**

See Section [10.3.3.1](#)

**10.3.3.10. Effectiveness non-inferiority: MenABCWY vs. rMenB+OMV NZ**

Analysis set: PPS will be the primary analysis population.

Statistical method: The percentage of samples with bactericidal activity measured by enc-hSBA at 1:4 dilution and the corresponding exact two-sided 97.5% CIs based on Clopper-Pearson method will be calculated for the ABCWY (pooled lots) group and the Men B group. The 97.5% CIs for the difference in percentages between ABCWY (pooled

**CONFIDENTIAL**205416 [MENB REC 2ND GEN-038 (V72\_72)]  
Protocol Amendment 4 Final

lots) and MenB group will be constructed using the method of Miettinen and Nurminen [Miettinen, 1985].

Non-Inferiority criterion: Non-inferiority of MenABCWY vaccine for the percentage of samples with bactericidal activity measured by enc-hSBA at 1:4 dilution will be demonstrated if the lower limit of the two-sided 97.5% CI for the difference between the 2 groups (ABCWY (pooled) lots – MenB) is above -5%.

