### 10.1.1. Hypothesis testing strategy

Multiple objectives and endpoints require type I error control. Full alpha (0.05) is split equally (alpha=0.025) between rMenB+OMV NZ objectives and MenABCWY objectives. Furthermore, within rMenB+OMV NZ, as well as within MenABCWY, objectives are tested hierarchically. If the first null hypothesis is rejected, then the testing will continue with the second hypothesis at same alpha. Same for 3rd, 4th, and so forth. Whenever a null hypothesis is not rejected, then the testing will stop.

As the comparator for MenABCWY non inferiority objective for the B component will be the selected schedule of rMenB+OMV NZ as determined in this study, the objectives of rMenB+OMV NZ will be analysed first. Additionally, if all null hypotheses related to rMenB+OMV NZ objectives will be rejected, the alpha (alpha=0.025) will be propagated to the MenABCWY part, and hypotheses related to MenABCWY objectives will be tested at full alpha (alpha=0.05). See Figure 2 for an explanation of the hierarchical testing (top to bottom, the order indicated by the arrows).

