**10.1.1.10. Effectiveness non-inferiority: MenABCWY vs. rMenB+OMV NZ**

For demonstration of non-inferiority of the VE of MenABCWY compared to the VE of rMenB+OMV NZ the following hypothesis will be tested:

*Null hypothesis:*

$$H_0: \pi_{ABCWY} - \pi_{Control} \leq -5\%$$

vs.

*Alternative hypothesis:*

$$H_1: \pi_{ABCWY} - \pi_{Control} > -5\%$$

**CONFIDENTIAL**205416 [MENB REC 2ND GEN-038 (V72\_72)]  
Protocol Amendment 4 Final

Where:  $\pi_{ABCWY}$  and  $\pi_{Control}$  represent the percentages of samples with bactericidal serum activity at 1:4 dilution in the ABCWY group (pooled lots) 1 month after the last MenABCWY vaccination and in the MenB group one month after the last rMenB+OMV NZ vaccination of the final schedule as determined in this study; and -5% is the non-inferiority margin for the difference in percentages of samples with bactericidal serum activity between ABCWY (pooled lots) and MenB group. Non inferiority of MenABCWY to rMenB+OMV NZ will be claimed if the LL of the 2-sided 97.5% CI for the group difference in percentages of samples with bactericidal serum activity at 1:4 dilution is above -5%.

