**10.1.2.1. Vaccine effectiveness (Test-based): rMenB+OMV NZ - 3 doses (0,2,6-months schedule)**

The planned (target) number of strains to be tested for each subject will be 35 strains. A minimum amount of 5 mL of serum needs to be available to perform enc-hSBA testing. In case the volume of serum shipped to the laboratory for enc-hSBA testing is <5 mL, enc-hSBA testing will be still performed if the volume of serum allows to test a minimum number of 20 strains. Otherwise no enc-hSBA testing will be performed with the specific sample. The power was calculated for two situations: 30 and 35 strains to be tested per subject.

In study V102\_16E1, the observed raw percentages of samples without bactericidal serum activity at 1:4 dilution were 77.8% in the MenACWY vaccine group and 21.9% in the MenABCWY group one-month post 3rd vaccination. The estimated VE of MenABCWY compared to MenACWY was 71% (95% CI: 69% - 73%). For the sample size calculations, it is assumed that MenB (any schedule) will have similar results as MenABCWY 0,2,6-months.

[Table 18](#) shows the result of power calculation for a group size of 684 evaluable subjects in MenB group, (any schedule) and 137 subjects in MenACWY group. The percentage of tests without bactericidal serum activity for MenACWY is assumed to be 75%, while the estimation for MenB is 22%. Sample size calculations revealed >99.9% power to show that the lower limit of the two-sided 97.5% CI for the VE is >65% (Refer to Section [10.1.1.1](#))

**CONFIDENTIAL**205416 [MENB REC 2ND GEN-038 (V72\_72)]  
Protocol Amendment 4 Final**Table 18 Power for VE 65% against all 110 strains combined, any schedule**

% of tests without bactericidal serum activity at 1:4 dilution		Power			
MenACWY	MenB	Vaccine Effectiveness	Success Criterion (LL of 97.5% CI)	30 strains per subject	35 strains per subject
75%	20%	73%	>65%	99.9%	99.9%
77%	20%	74%	>65%	99.9%	99.9%
75%	22%	71%	>65%	99.9%	99.9%
77%	22%	71%	>65%	99.9%	99.9%
75%	25%	67%	>65%	84.4%	89.3%
77%	25%	68%	>65%	99.8%	99.9%

LL: lower level, CI: Confidence Interval, VE: Vaccine Effectiveness

\* Computed by 10,000 simulation runs each based on SAS GENMOD procedure.

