**10.1.2.10. Effectiveness non-inferiority: MenABCWY vs. rMenB+OMV NZ**

The target number of evaluable subjects of 684 (in ABCWY group (pooled lots)) and 684 (in the Control group) at 1 month after the last vaccination is sufficient to demonstrate that the lower limit of the two-sided 97.5% CI for the difference in percentages of samples with bactericidal activity at 1:4 dilution in the ABCWY group (pooled lots) and in the Control group is above -5%.

Assuming the percentage of samples with bactericidal serum activity at 1:4 dilution in ABCWY group (pooled lots) 75% and 75%-78% in MenB, the power to show non-inferiority is  $\geq 99.8\%$ . ([Table 22](#)).

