**10.3.3.1. Vaccine effectiveness (Test-based): rMenB+OMV NZ - 3 doses (0,2,6-months schedule)**

Analysis set: Per-protocol set (PPS) will be the primary analysis population

Statistical method: The VE is defined as  $1 - RR = (1 - \text{percentage of samples without bactericidal serum activity at 1:4 dilution in MenB group} / \text{percentage of samples without bactericidal serum activity at 1:4 dilution in the Control group}) \times 100\%$  and it will be analyzed using a generalised linear model with vaccine group, strain and centre as independent variables. Furthermore, a repeated statement will be used to estimate the variance of the RR including correlation within subject's responses. A centre effect will be tentatively included in the analysis; if the statistical model does not converge due to

**CONFIDENTIAL**205416 [MENB REC 2ND GEN-038 (V72\_72)]  
Protocol Amendment 4 Final

the factor “centre”, a model without centre effect will be fitted instead. The response variable of the model will be the Bernoulli distributed outcome without bactericidal activity at a 1:4 dilution (i.e. response is 1 if titre < 4, and 0 if titre ≥ 4), at 1 month after the last vaccination (Month 7) in the MenB group and at Month 1 for the ACWY group. Each subject will contribute with approximately 35 measures to this analysis, each of the measures corresponding to the response variable to one of the 35 strains randomly assigned to be tested with the samples available for that specific subject. For the statistical analysis it is assumed that the response to each strain is an independent measure with a unique true underlying rate and VEs are expected to vary among the strains. In order to obtain the VE measure which is a measure based on the relative risk (RR), a generalised linear model will be used with the Binary distribution and link function log in order to compute the log RR and the corresponding 97.5% CI. If this model would not converge, the Poisson distribution will be used instead. The obtained values will be exponentiated to obtain the RR and the corresponding 97.5% CI. The VE will be computed as  $100\% \times (1 - RR)$ . Effectiveness of rMenB+OMV NZ will be demonstrated if the lower limit of the two-sided 97.5% CI for VE against the selected strain panel between MenB and the ACWY group is above 65%.

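### The MenABCWY versus rMenB+OMV NZ effectiveness non-inferiority test ignores within-subject correlation across about 35 strain results per subject, so its interval is too narrow and its error rate is not held

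*Protocol*

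**What the plan says.** Section 10.3.3.10 of the protocol compares MenABCWY (pooled lots) with the selected rMenB+OMV NZ schedule. The outcome is the pooled percentage of enc-hSBA samples with killing at 1:4. The named methods are "The percentage of samples with bactericidal activity measured by enc-hSBA at 1:4 dilution and the corresponding exact two-sided 97.5% CIs based on Clopper-Pearson method" for each group and a Miettinen-Nurminen interval for the difference. Non-inferiority is claimed if the lower limit exceeds -5%. No term for repeated results within a subject is mentioned.

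A sample here is one serum tested against one strain. Section 10.1.2.1 states: "The planned (target) number of strains to be tested for each subject will be 35 strains". The power calculation in section 10.1.2.10 takes 684 evaluable subjects per group and reads: "Assuming the percentage of samples with bactericidal serum activity at 1:4 dilution in ABCWY group (pooled lots) 75% and 75%-78% in MenB". Table 22 gives power of >99.9% for true differences of 0, -1 and -2 points, 99.8% for -3 and 64% for -4.

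Section 10.3.3.1 handles the same kind of data differently. For test-based vaccine effectiveness (VE), "a repeated statement will be used to estimate the variance of the RR including correlation within" a subject's responses.

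On the error level, section 10.1.1 says: "Full alpha (0.05) is split equally (alpha=0.025) between rMenB+OMV NZ objectives and MenABCWY objectives". That gives a 97.5% interval, or 1.25% one-sided. If all rMenB+OMV NZ hypotheses are rejected, the MenABCWY tests move to the full 0.05, or 2.5% one-sided.

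**The concern.** All results from one serum share that subject's antibody and that subject's own complement, so a strong responder tends to kill many strains and a weak one few. Positive correlation is the natural expectation, and the protocol allows for it in the VE model. An interval that treats every result as a separate subject has too small a standard error.

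In a non-inferiority test this favours the new vaccine: the lower limit sits too close to the estimate and clears -5% too often when the truth is -5%. This is a primary hypothesis in the alpha-controlled sequence, so the nominal level is part of the claim. The planned power is overstated for the same reason.

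**Working it through.** **1. Reproducing Table 22.** Inputs: margin 0.05; 684 subjects per group; 35 results per subject; two-sided alpha 0.025, so z = 2.2414; MenABCWY rate pT = 0.75; control rate pC from 0.75 to 0.79.

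SE = sqrt{[pC(1-pC) + pT(1-pT)]/n}; power = Φ((0.05 - (pC - pT))/SE - z).

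With n = 684 x 35 = 23,940 independent results:
- 75% vs 78%: SE = sqrt(0.3591/23,940) = 0.003873; 0.02/0.003873 - 2.2414 = 2.92; power 99.8%.
- 75% vs 79%: SE = sqrt(0.3534/23,940) = 0.003842; 0.01/0.003842 - 2.2414 = 0.36; power 64.1%.
- The other three rows exceed 99.9%.

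Every row matches. Simulating the Miettinen-Nurminen limit under independence also gives 99.8% and 64.1%. With n = 684 the five rows would be 45.8%, 30.1%, 17.3%, 8.6% and 3.6%. Table 22 therefore counts individual tests and treats them as independent.

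**2. How large might the correlation be?** The protocol states no intraclass correlation (ICC), so this is an assumption. Sections 10.1.2.1 and 10.1.2.2 report, for study V102_16E1 after the third dose, 21.9% of samples not killed (78.1% killed) and 78.5% of subjects killing at least 70% of strains (95% CI 68.8% to 86.3%).
- Assume 35 strains per subject, so a responder kills at least 25.
- Independence: P(Binomial(35, 0.781) ≥ 25) = 87.5%, above the upper confidence limit of 86.3%.
- A beta-binomial with mean 0.781 reproduces 78.5% at ICC = 0.039.
- Design effect: DE = 1 + (35 - 1) x 0.0387 = 2.32; sqrt(DE) = 1.52.

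The planning pairs also imply positive values: 75% killed with 72.5% responders gives about 0.013, and 78% with 72.5% about 0.12.

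**3. Actual one-sided error at a true difference of -5 points.** The unadjusted limit has error 1 - Φ(z/sqrt(DE)). At DE 2.32:
- nominal 1.25%: 1 - Φ(2.2414/1.52) = 7.0%
- nominal 2.5%: 1 - Φ(1.960/1.52) = 9.9%
- two-sided coverage of the nominal 97.5% interval: 1 - 2 x 7.0% = about 86%

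Beta-binomial simulation of the Miettinen-Nurminen limit (20,000 runs) agrees: 4.1% at ICC 0.02, 8.3% at 0.05 and 14.2% at 0.10, against formula values of 4.2%, 8.6% and 14.3%.

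**4. Power with a correct standard error.** Multiply SE by sqrt(DE), keeping z = 2.2414.

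| DE | Error, nominal 1.25% | Error, nominal 2.5% | Power 75 vs 77 | Power 75 vs 78 | Power 75 vs 79 |
|---|---|---|---|---|---|
| 1 (Table 22) | 1.25% | 2.5% | >99.9% | 99.8% | 64% |
| 1.5 | 3.4% | 5.5% | >99.9% | 97.6% | 45% |
| 2.32 | 7.0% | 9.9% | 99.7% | 87.5% | 30% |
| 5 | 15.8% | 19.0% | 88% | 53% | 14% |

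**The case against.** Four points can be made for the plan.

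- **Earlier gate.** The MenABCWY hypotheses are tested in sequence. In section order, test-based VE (lower limit above 65%) comes before this test, and it does adjust for correlation. At 73% killed against 78%, VE with the planned 75% control rate is 1 - 27/75 = 64%, below that gate's own null. The chance of passing the gate at DE 2.3 is about 0.01% at a control rate of 75%, 1.0% at 77% and 3.5% at 77.8%. In that scenario a false claim would usually be stopped earlier. This stands, but it depends on the absolute rates. If the true rates were 78% against 83%, the gate would pass and the inflation would apply in full.
- **Alpha branch.** The protocol plans 90% power to reject all rMenB+OMV NZ hypotheses, so 2.5% one-sided is the more likely level. This also stands. The inflation is then about fourfold (9.9% against 2.5%) instead of nearly sixfold.
- **Uncertain ICC.** The estimate rests on one post-hoc responder rate. Its upper confidence limit gives an ICC of about 0.003. Assuming 20, 25 or 30 strains per subject in the prior study moves the estimate to 0.069, 0.027 or 0.066. The single figures are therefore illustrative. All these values are still positive.
- **Little effect near zero difference.** At DE 2.3, power stays above 99% down to a true difference of -2 points. That is true, but it does not restore the error rate at the margin.

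Drawing strains at random without replacement adds only a small negative correlation and does not offset the subject effect.

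**Conclusion.** The method is wrong as written. Section 10.3.3.10 fixes independent-binomial intervals for data with about 35 correlated results per subject, and it conflicts with the protocol's own handling of the same assay in section 10.3.3.1. Table 22 is arithmetically correct for its model; the independence assumption is the fault.

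The direction of the error is clear, but its size is conditional. It rests on equal clusters of 35, a common ICC in both groups and a beta-binomial reading of the prior-study figures. These error rates belong to this test taken alone; the VE gate may lower the chance of a false claim in practice but does not make the interval valid. Because the nominal level of a primary hypothesis is affected, this must be corrected before the analysis.

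**What to change.** In section 10.3.3.10 and the statistical analysis plan, replace the Clopper-Pearson and Miettinen-Nurminen intervals by a subject-clustered analysis. One suitable form is a GEE with vaccine group and strain as factors, subject as cluster and robust variance. The risk difference comes from an identity link or marginal standardisation, and its lower limit is tested against -5% at whichever confidence level the alpha rule gives. A cluster-adjusted score interval or a cluster bootstrap would also serve. The choice should be fixed before unblinding.

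Recompute Table 22 with a stated ICC and a range around it, and check the overall 92% power for the MenABCWY objectives in section 10.1 against the result.

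The cost is wording and a less favourable power table. The data, sample size and visits are unchanged.

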**10.3.3.11. Effectiveness (Responder-based): MenABCWY**

See Section [10.3.3.2](#)

**10.3.4. Secondary effectiveness and immunogenicity analyses****10.3.4.1. Immunological non-inferiority: MenABCWY vs. rMenB+OMV NZ**

(Amended 9 May 2021)

Analysis set: PPS will be the primary analysis population.

Statistical method: The percentages of subjects with 4-fold rise in hSBA titres against *N. meningitidis* serogroup B indicator strains (M14459, 96217, **M13520** and NZ98/254 for fHbp, NadA, NHBA and PorA P1.4 antigens, respectively) at 1 month after the last vaccination for the ABCWY group (pooled lots) (Day 211, Month 7) and 1 month after the 3-dose vaccination series (Day 211, Month 7) in MenB\_0\_2\_6 group or 2-dose vaccination series (Day 211, Month 7) in MenB\_0\_6 group or 2-dose vaccination series (Day 91, Month 3) in MenB\_0\_2\_6 group and the corresponding exact 2-sided 95% CIs based on Clopper-Pearson method will be calculated [Clopper, 1934]. The 95% CIs for the difference in percentages between ABCWY group (pooled lots) and MenB\_0\_2\_6 group and MenB\_0\_6 group will be constructed using the method of Miettinen and Nurminen [Miettinen, 1985].

Non-inferiority criterion: Non-inferiority of MenABCWY vaccine for the proportion of subjects with 4-fold rise will be demonstrated if the lower limit of the 2-sided 95% CI for the difference in percentage of subjects with 4-fold rise between the 2 groups (ABCWY group (pooled lots) – selected MenB group) is above -10%.

**10.3.4.2. Effectiveness by each of the endemic US *N. meningitidis* serogroup B strains**

Analysis set: FAS effectiveness will be the primary analysis population. A subset (VE subset) of approximately 684 evaluable subjects per group, ABCWY (pooled lots) and of the MenB\_0\_2\_6 or MenB\_0\_6 group would be used for the purpose of this analysis.

Statistical method: The VE per strain will be calculated as described in Section [10.3.3.1](#), using a generalised linear model with vaccine group, and centre as independent variables.

**CONFIDENTIAL**205416 [MENB REC 2ND GEN-038 (V72\_72)]  
Protocol Amendment 4 Final**10.3.4.3. Distribution of percentages of serogroup B invasive disease strains killed**

Analysis set: FAS effectiveness will be the primary analysis population. A subset (VE subset) of approximately 684 evaluable subjects per group, ABCWY (pooled lots) and of the MenB\_0\_2\_6 or MenB\_0\_6 group would be used for the purpose of this analysis.

Statistical method: The distribution will be presented of subjects by percentages of serogroup B invasive disease strains killed using enc-hSBA at 1 month after the 3-dose (0,2,6-months in MenB\_0\_2\_6 group) and 2-dose (0,6-months in MenB\_0\_6 group, 0,2-months in MenB\_0\_2\_6 group and 0,6-months in the ABCWY (pooled) group) vaccination series of rMenB+OMV NZ and MenABCWY vaccines.

Summary statistics and 95% CI for the mean percentage will be presented, as well as a Figure of the cumulative distribution function.

**10.3.4.4. Immune response of MenABCWY, rMenB+OMV NZ and MenACWY****(Amended 9 May 2021)**

Analysis set: The analysis will be based on the FAS.

Statistical method: The hSBA titres at each time point for all groups (ABCWY group (pooled lots), MenB\_0\_2\_6 and MenB\_0\_6 groups) will be logarithmically transformed (base10) to fulfil the normal distribution assumption. For each *N. meningitidis* serogroup A, C, W and Y and each B indicator strain (M14459, 96217, **M13520** and NZ98/254 for fHbp, NadA, NHBA and PorA P1.4 antigens, respectively), the GMTs and GMRs (post-vaccination/baseline) will be calculated with their associated 2-sided 95% CIs, by exponentiating the corresponding log-transformed means and their 95% CIs. The ratio of GMTs and GMRs between two groups and the corresponding CI will be constructed by exponentiating the mean difference and the confidence limits in log10 (titre), using ANOVA with study centre included as an independent variable.

The total IgG as measured by ELISA GMCs against serogroups A, C, W and Y at baseline (Day 1, Month 0) and

- at 1 month after the first (Day 31, Month 1) and the last vaccination (Day 211, Month 7) for the ABCWY group (pooled lots), and
- at 1 month after the MenACWY vaccination in the ACWY group (Day 31, Month 1),

will be analyzed in a comparable way as described above for hSBA titres.

For each *N. meningitidis* A, C, W and Y and each serogroup B indicator strain (M14459, **M13520**, 96217 and NZ98/254) the percentages of subjects with hSBA titres  $\geq$  LLOQ and of subjects with 4-fold rise and the corresponding exact 2-sided 95% CIs based on Clopper-Pearson method will be calculated for each study group at each timepoint not previously analyzed.

**CONFIDENTIAL**205416 [MENB REC 2ND GEN-038 (V72\_72)]  
Protocol Amendment 4 Final**10.3.5. Safety analyses**

Distribution of subjects by vaccinations will be summarised by vaccine group for the Enrolled Set. In case of vaccination error, subjects will be analyzed “as treated” (according to the vaccine the subject actually received).

**Analysis sets:** Solicited Safety Set (solicited local and systemic adverse events and other solicited adverse events), Unsolicited Safety Set (unsolicited adverse events), and Overall Safety Set.

Endpoint	Statistical Analysis Methods
Primary	
Endpoints description: The frequencies and percentages of subjects with solicited local (i.e., injection site pain, erythema, swelling, induration) and systemic (i.e., fever [temperature <math>\geq 38.0^{\circ}\text{C}</math>], nausea, fatigue, myalgia, arthralgia, headache) adverse events during the 7 days (including the day of vaccination) following each vaccination at Day 1, Day 61 and Day 181.
 
All solicited adverse events will be summarised according to defined severity grading scales, see protocol section 12.5.9.3
 
Frequencies and percentages of subjects experiencing each adverse event will be presented for each symptom severity. Summary tables showing the occurrence of any local or systemic adverse event overall and at each time point will also be presented.
 
Post-vaccination solicited adverse events reported from Day 1 to Day 7 will be summarised for the intervals Day 1-3, Day 4-7, and Day 1-7 by maximal severity and by vaccine group, excluding the 30-minute measurement, which will be summarised separately. The severity of solicited local adverse events, including redness (erythema) at injection site, swelling of skin at injection site, and hardness of skin at injection site will be summarised according to categories based on linear measurement: None (1 to 24mm); Mild (25 to 50mm); Moderate (51 to 100mm); Severe (>100mm).
 
Injection site tenderness and systemic reactions (except fever) occurring up to 7 days after each vaccination at Day 1, Day 61 and Day 181 will be summarised according to “mild”, “moderate” or “severe”.
 
Each solicited local and systemic adverse event will also be further summarised as “none” versus “any” (for fever the latter will be <math>\geq 38.0^{\circ}\text{C}</math>).
 
Use of antipyretics and analgesics will be summarised by frequency by type of use (prophylactic versus treatment) and percentage of subjects reporting use.
 
Body temperature will be summarised by <math>0.5^{\circ}\text{C}</math> increments from <math>36.0^{\circ}\text{C}</math> up to <math>\geq 40^{\circ}\text{C}</math> and will be broken down according by route of measurement, if applicable. Frequencies and percentages of subjects with temperatures <math>\geq 38.0^{\circ}\text{C}</math> and temperatures <math>\geq 40.0^{\circ}\text{C}</math> will also be presented.

	
Endpoints description: The frequencies and percentages of subjects with any unsolicited AEs (including all SAEs), AEs leading to withdrawal and medically attended AEs during the 7 and the 30 days (including the day of vaccination) following each vaccination at Day 1, Day 61 and Day 181.
 
The frequencies and percentages of subjects with SAEs, AEs leading to withdrawal, AESIs and medically attended AEs throughout the study period.
 
This analysis applies to all adverse events occurring during the study, judged either as possibly related, or not related to vaccination by the investigator, recorded in AE CRF, with a start date on or after the date of first vaccination. AE starting prior to the first vaccination will only be listed. The original verbatim terms used by investigators to identify adverse events in the CRFs will be mapped to preferred terms using the MedDRA dictionary. The adverse events will then be grouped by MedDRA preferred terms into frequency tables according to system organ class. All reported adverse events, as well as adverse events judged by the investigator as possibly related to study vaccine, will be summarised according to system organ class and preferred term within system organ class. These summaries will be presented by vaccine group and by interval of study observation. When an adverse event occurs more than once for a subject, the maximal severity and strongest relationship to the vaccine group will be counted.

